9.2.3 Oral mucose swab (mouth swab)

To obtain the sample, the professional will rub a buccal swab against the inside of the patient's cheeks and gums, and place it in a dry sterile 1.5ml eppendorf-type tube with lysis buffer; once labeled with the participant's ID, it will be placed in the refrigerator at 4°C waiting to be sent to the laboratory, where the DNA extraction will be performed. Subsequently, it will be stored in a freezer at -20°C.

9.2.4 Coronary Computed Tomography Angiography

Participants' donated CCTA images and associated data will be collected and anonymised at the site for further analysis.

CCTA acquisition protocols will follow each site's standard procedures. The use of any medications involved in routine CCTA examinations such as beta blockers (in the case of a heart rate higher than 65 beats per minute) or sublingual nitroglycerin will not be encouraged, the decision being left at the discretion of the physician involved in the acquisition. CTCA images will be transferred to an AWS server for independent data analysis.

9.3. Sample processing and sequencing

Blood samples will be processed after extraction using commercial kits for RNA extraction. Subsequently, the *library*, a procedure by which the transformation of the RNA sample into short cDNA chains for sequencing is known. For this procedure, the commercial kit TruSeq-RiboZero-GlobinFree (Illumina) will be used. Subsequent sequencing (without ribosomal RNA and globin) will be performed by an external sequencing service provider. A sequencing with a read depth of at least 100 million reads will be requested.

9.4. Bioinformatic and computational analysis of the transcriptomics sample

The bioinformatic analysis of the sequenced samples will be performed from the .fastq files containing the raw data. These files will be fed to a *pipeline* analysis which comprises a successive series of bioinformatic procedures, including sample quality control, alignment with the human genome and count of *reads* per identified gene. The transcripts to be identified correspond to:

- Linear RNA identification, including mRNA and non-coding RNAs.
- circRNA (circular RNA)
- Alternative splicing variant identification
- Blood microbiome
- Variant calling for Polygenic risk score calculation (from RNA).

The expression quantification of the transcripts is then transformed using a series of proprietary routines, to then be transformed into an image (US patent 62/944,063 (pending)). This image represents both the expression of the transcripts as a function of their expression level and the genomic position as well as the RNA subtype. The set of images, which represent the set of gene expression in peripheral blood, is subsequently entered into a neural network to generate training that classifies the samples accordingly.

Once the bioinformatic analyses are done, we will use that information to train machine and deep learning models to predict those patients with coronary artery disease. The following ML/DL approaches will be used:

- Classical machine learning algorithms, including xgboost.
- Convolved Neural Networks (CNN) through our patented technology of gene expression conversion.
- Graph neural networks.
- Natural processing language by using reads.

All these bioinformatic and artificial intelligence procedures will be carried out using free-use programs (“open access software”) under a routine created by the study

researchers, mainly using python for coding and pyTorch for the training of the neural network.

Data will be stored and analyzed at the cloud provider at the moment of analysis (currently AWS or Google Cloud) under strict cybersecurity measures.

9.5. Analysis of Coronary Computed Tomography Angiography

Coronary Calcium scoring will be analyzed using dedicated software (HeartBeat-CS, Philips Healthcare, Best, The Netherlands) by an experienced observer blinded to the clinical characteristics, laboratory, and transcriptome results. The presence of CAC and its extension will be evaluated using both ordinal variables (number of segments with CAC and number of affected vessels, and qualitatively: absence, mild, moderate, and severe) and continuous variables (Agatston units). The presence and extension of calcifications at the level of the aortic valve and the thoracic aorta (Agatston units) will also be evaluated independently. The extent of aortic calcification will be evaluated in sections that include the area ranging from the bifurcation of the pulmonary artery as the upper limit to the diaphragm as the lower limit.

CCTA images will be anonymised locally and transferred to a core laboratory located in Oxford, UK, for analysis of secondary outcomes by investigators who will be unaware of population demographics and outcomes. The presence of obstructive CAD will be defined as the presence of at least one lesion causing a luminal stenosis of 50% or larger. The extent of coronary artery disease using the modified Duke coronary artery disease index, as follows (Group 1: <50% stenosis; Group 2: ≥ 2 mild stenosis with proximal CAD in 1 artery or 1 moderate stenosis; Group 3: 2 moderate stenosis or 1 severe stenosis; Group 4: 3 moderate stenosis, 2 severe stenosis, or severe stenosis in the proximal left anterior descending (LAD) artery; Group 5: 3 severe stenosis or 2 severe stenosis in the proximal LAD; Group 6: $\geq 50\%$ stenosis in left main coronary artery). The presence of high-risk plaque features (spotty calcification, low-attenuation plaque, positive remodeling, and napkin-ring sign) will be explored. The total epicardial adipose tissue volume will be calculated in a semi-automated manner by tracking the contour of the pericardium from

the level of the pulmonary artery bifurcation to the apex of the heart at the most caudal end. To measure the perivascular FAI, we will trace the proximal 40-mm segments of all three major epicardial coronary vessels (right coronary artery, left anterior descending artery, and left circumflex artery) and defined respective perivascular fat as the adipose tissue within a radial distance from the outer vessel wall equal to the diameter of the vessel, as described and validated previously. To avoid the effects of the aortic wall, we excluded the most proximal 10 mm of the right coronary artery and analyzed the proximal 10–50 mm of the vessel, as described previously. In the left anterior descending artery and left circumflex artery, we will analyze the proximal 40 mm of each vessel.

As follows, 3-dimensional plaque quantification of the whole vessel will be performed (10,13) using semi-automated plaque analysis software. All IDs will undergo double reading of the main outcome of the study (presence or extent of CACs). This reading will be carried out by an expert external to the group of researchers of the study and blind to the first reading. In case of disagreement, consensus will be sought between the two experts. The aim of this process is to enhance the internal validity of the study.

9.6. Storage of biological samples

The remnant of the RNA samples and all of the DNA samples will be stored in a freezer at -20° C to be used in future research. The biological samples will be coded (see Confidentiality of the data) to maintain the anonymity of the participants and will be stored at the laboratory. The storage place has the necessary equipment to ensure their proper preservation. The temperature and other storage conditions will be permanently monitored as part of the quality assurance of the biological samples. It also has an emergency plan with trained personnel with defined responsibilities to attend to alarms and take actions to restore the system in the event of a failure. The freezer that preserves the biological samples and the monitoring systems are connected to a permanent electrical source, with an emergency generator with enough autonomy to ensure its uninterrupted operation.

Since the stored samples will not be used in this study, specific consent will be requested for their storage and subsequent analysis.

9.7. Patient follow-up

Patients included in the study will be contacted annually by phone call or email to collect the following data:

- Vital status.
- Cardiovascular events: New episodes of hospitalization due to acute ischemic syndrome, cerebrovascular event, heart failure or revascularization.
- New diagnoses of relevant chronic diseases.

If they cannot be contacted, the "alternative means of contact" provided by the patient will be used, in order to know their vital status or obtain a new contact number.

9.7.1. Events of interest in the study during follow-up

The study will assess the following incident events:

- Death from any cause.
- Fatal and non-fatal atherosclerotic related events: AMI, angina, cerebrovascular accident ("stroke") or transient ischemic attack.
- Hospitalized (emergency room or admitted) Heart failure event with preserved or impaired ventricular function.
- Vascular revascularization: performance of myocardial revascularization surgery, coronary angioplasty or peripheral vascular angioplasty.
- Cancer: new diagnosis of any type of cancer.

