6.1 Primary Objective

The main objective of this study is to investigate the diagnostic accuracy of whole-blood transcriptome analyzed by artificial intelligence in detecting the presence and extent of coronary atherosclerosis in stable patients with suspected or known coronary artery disease (CAD), using coronary computed tomography angiography (CCTA) images.

Specific aims:

I) To classify patient transcriptomes based on the presence and extent of the following CCTA outcomes:

- Coronary calcium score
- Total coronary plaque burden
- Degree of coronary stenosis
- Coronary high-risk plaques (low-attenuation, positive remodeling; spotty calcification, or napkin-ring sign)

II) To train artificial intelligence algorithms using information from the transcriptome to recognize the outcomes of interest in the training set.

III) To explore the diagnostic accuracy (sensitivity and specificity) of the method in detecting the presence, absence, or extent of the outcomes of interest in the validation/test set.

6.2 Secondary Objectives:

The secondary objectives of this study are as follows:

6.2.1 To explore the diagnostic accuracy of whole-blood transcriptome in relation to other outcomes of interest provided by CCTA images, including:

- Presence and extent of aortic calcification
- Hepatic steatosis
- Flow limiting artery obstruction (coronary fractional flow reserve)
- Coronary artery inflammation (perivascular fat attenuation index)
- Total epicardial adipose tissue volume

6.2.2 To calculate the polygenic risk score (PRS) from the transcriptome and explore its association with the previously described outcomes of interest.

6.2.3 To explore the differences in transcriptomics of peripheral blood between patients who did and did not develop a cardiovascular event during follow-up.

7. Methods

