7.1. Study Design

This will be a prospective observational study. A convenience sample will be carried out to include 200 patients who attend the ENERI Medical Institute, La Sagrada Familia Clinic and Sanatorio Mendez with a clinical indication to be evaluated by a CCTA due to suspected CAD or known CAD. The study will have a baseline stage in which a clinical evaluation will be performed, blood samples will be drawn for transcriptome analysis and laboratory analysis. Then, a DNA sample obtained by swabbing the buccal mucose will be taken. Subsequently, the images obtained from the clinically indicated CCTA will be assessed to explore the outcomes of interest. At the end of patient enrollment, biological samples will be sequenced for in silico evaluation of the results. Finally, a 5-year follow-up will be carried out via telephone or email contact to collect data on the incidence of fatal and non-fatal cardiovascular events.

8. Study Population

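### Sections 9.7 and 9.7.1 set no condition on why or when a revascularisation is done, so procedures prompted by the index CCTA may count as events for objective 6.2.3 and the contrast can partly repeat baseline stenosis

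*Protocol*

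**What the plan says.** Objective 6.2.3 is "To explore the differences in transcriptomics of peripheral blood between patients who did and did not develop a cardiovascular event during follow-up". It is listed under the secondary objectives and worded as exploratory.

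Two sections of the Protocol bear on what such an event is:

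- Section 9.7, on the annual contacts, collects "Cardiovascular events: New episodes of hospitalization due to acute ischemic syndrome, cerebrovascular event, heart failure or revascularization".
- Section 9.7.1 lists the incident events of interest, among them "Vascular revascularization: performance of myocardial revascularization surgery, coronary angioplasty or peripheral vascular angioplasty".

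Neither restricts the reason for a procedure or its distance in time from the scan. Section 9.7.2 has adjudicators work from the type, date, place and source document of each event, and gives no rule for procedures that follow from the baseline scan. The time limits on interventions in section 8.2 are exclusions that look back from entry.

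Section 7.1 recruits patients "with a clinical indication to be evaluated by a CCTA due to suspected CAD or known CAD" and takes blood at baseline. Section 6.1 already includes "Degree of coronary stenosis" among the primary-objective outcomes read from that scan, and section 9.5 defines obstructive disease as at least one stenosis of 50% or more.

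**The concern.** In this cohort the scan is both the entry ticket and a clinical test whose result can lead to treatment. A patient with an obstructive lesion at baseline may be referred for angioplasty or bypass because of that lesion. The procedure is new, and it meets the wording of both sections. It then records disease that was present when blood was drawn, not something that developed afterwards.

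If such patients sit in the event group, a transcriptomic difference found under 6.2.3 can be partly the cross-sectional stenosis signal of the primary objective under another name. A reader would take it as a finding about later events. What is at stake is the interpretation of this one secondary contrast, which the five years of follow-up and the adjudication committee serve.

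**Working it through.** The protocol states no event rate, event count or power for 6.2.3, so there is no figure of its own to reproduce. The check has two parts.

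**1. Does the wording admit scan-prompted procedures?**

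- Sections 9.7 and 9.7.1 use words for new or incident events. These exclude past procedures; one done after the index scan is still new.
- Section 9.7 adds hospitalisation, which is a condition neither on indication nor on interval. Section 9.7.1 does not repeat it.
- Section 8.2 limits only interventions before entry.
- Section 9.7.2 contains no exclusion.
- Sections 7.1 and 10.13 define no day zero for a patient.

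So nothing excludes these procedures, and nothing settles that all of them fall inside follow-up.

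**2. How large could the effect be?** Only N = 200 (section 7.1) comes from the protocol. The rest are assumptions:

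- o: share with obstructive disease, 25% (range 10–35%)
- r: share of those revascularised because of the scan, 30% (20–40%); only obstructive patients have such procedures
- a: average annual rate of other events, 2% (1–3%), over 5 years
- k: ratio of the annual rate of other events, obstructive to non-obstructive, 1 or 3

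Formulas:

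- annual rates: an = a / (o·k + 1 − o) without obstruction, ao = k·an with it
- five-year risks: qn = 1 − (1 − an)^5, qo = 1 − (1 − ao)^5
- patients with a scan-prompted procedure = 200·o·r
- of these, with no other event (scan-only) = 200·o·r·(1 − qo)
- patients with another event = 200·o·qo + 200·(1 − o)·qn

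Middle case, k = 1:

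- qn = qo = 1 − 0.98^5 = 0.096
- scan-prompted = 200 × 0.25 × 0.30 = 15.0; scan-only = 15.0 × 0.904 = 13.6
- other events = 200 × 0.096 = 19.2, of which 50 × 0.096 = 4.8 in obstructive patients
- event group = 13.6 + 19.2 = 32.8; scan-only share = 13.6 / 32.8 = 41%
- obstructive share of the event group: 4.8 / 19.2 = 25% without scan-only patients, (13.6 + 4.8) / 32.8 = 56% with them

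Middle case, k = 3:

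- an = 0.02 / 1.5 = 0.0133, ao = 0.04; qn = 0.065, qo = 0.185
- scan-only = 15.0 × 0.815 = 12.2
- other events = 50 × 0.185 + 150 × 0.065 = 9.2 + 9.7 = 19.0 (before rounding)
- event group = 31.2; scan-only share = 12.2 / 31.2 = 39%
- obstructive share: 9.2 / 19.0 = 49% without, (12.2 + 9.2) / 31.2 = 69% with

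Over the grid (o = 10, 15, 25, 35%; r = 20, 30, 40%; a = 1, 2, 3%), the scan-only share runs from 10.8% to 73.1% for k = 1 and from 8.9% to 72.4% for k = 3. The low end is o = 10%, r = 20%, a = 3%. The high end is o = 35%, r = 40%, a = 1%.

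**Side effect of setting scan-only patients apart** (k = 1): the no-event group keeps 35 × 0.904 = 31.6 obstructive and 150 × 0.904 = 135.6 other patients, so 31.6 / 167.2 = 19% are obstructive, against 25% in the cohort.

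**The case against.** **The event group is not fixed.** Section 9.7.1 also lists death from any cause and cancer, so it is a collection list and cannot itself be the 6.2.3 endpoint. Which events form the contrast may be settled in an SAP that is not shown. The first part stands. But section 9.7 does name revascularisation as a cardiovascular event, and 6.2.3 uses that same term. The protocol's own wording therefore admits these procedures.

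**Follow-up may start too late to catch them.** Section 7.1 mentions follow-up last, and the timeline in section 10.13 separates a 12-month baseline phase from follow-up years 1 to 5. Early procedures might fall outside. This stands as a limit: a reader might infer that all scan-prompted procedures enter the event group, but the documents support only that they may.

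**The order of steps in 7.1 proves nothing about treatment.** "Subsequently, the images obtained from the clinically indicated CCTA will be assessed to explore the outcomes of interest" describes the research reading of the images. A reader might take it to show that procedures come after the blood draw, but it does not date the scan or any treatment. That ordering rests on the usual sequence of scan and then treatment.

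**6.2.3 only explores differences.** It claims neither prediction nor independence from stenosis. True, and this limits the weight of the point. It does not remove the risk that the result is read as concerning later events.

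**The data are already collected.** Dates and source documents would allow sorting later. A date alone does not show what prompted a procedure, though, and nobody is asked to extract the reason. Recording it at adjudication is more reliable than reconstructing it years afterwards.

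**Flagging does not remove the overlap.** In the k = 3 case the event group is still 49% obstructive without scan-only patients, against 25% in the cohort. This stands, and it is why the flag needs an analysis that takes account of stenosis beside it.

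**Conclusion.** The point holds in a limited form. As worded, coronary procedures prompted by the index CCTA may count as events for 6.2.3, and the contrast can then partly repeat baseline stenosis. The direction is clear, provided that such procedures are done mainly in patients with obstructive disease. The size is not known. The 41% and 39% are illustrations, and the span of 9% to 73% shows how strongly they depend on assumed rates; none of them estimates what this study will see.

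A reader might also infer that the diagnostic-accuracy results are compromised. The documents do not support that: the primary objective uses the baseline scan and no follow-up events. The change is worth making because it is cheap and concerns a listed secondary objective. Confidence is medium, mainly because the start of follow-up and the exact event set are left open.

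**What to change.** 1. In section 9.7.2, have the adjudicators record, from the source documents already obtained, whether each coronary revascularisation was prompted by the index CCTA (yes or no).
2. Report the 6.2.3 contrast twice: with flagged procedures counted as events, and without. In the second version, keep patients whose only event is a flagged procedure as a separate category, not as no-event controls. A patient who also has another qualifying event stays in the event group.
3. Add an analysis of 6.2.3 stratified by or adjusted for baseline CCTA stenosis, which is already measured.
4. State the date from which follow-up events count for each patient.

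The cost is one adjudication field, a few sentences of text and two further analyses of existing data. The restricted version has fewer events (about 33 falling to 19 patients in the k = 1 illustration, with about 14 set apart). It also leaves a small imbalance, because the patients set apart are missing from the no-event group (19% obstructive instead of 25%). Some overlap with stenosis remains in any version, so the versions should be read side by side.

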10.1. Confidentiality of the data

The data of the patients will be collected anonymously from the moment of signing the informed consent. To do this, an ID code representative of the patient will be created, which will include the initials of the study, followed by a hyphen and the inclusion number. The clinical documentation of the patient and the tube containing the blood of the patients or control subjects will contain only this information. The informed consent will be kept in a different location from the clinical information and under lock and key.

The transcriptomics data will remain anonymized and will receive the name designated at the time of inclusion in the study. The data will be deposited and protected on AWS which is in compliance with the Health Insurance Portability and Accountability Act (HIPAA).

10.2. Data quality assurance and control

a. Data quality assurance and storage

This study will implement a standardized data collection process, since trained interviewers will ensure data collection uniformly across all respondents, properly fill out the forms and handle sensitive information.

Baseline data entry and storage will be performed using the electronic platform RedCap. This electronic data capture platform is covered by security systems, in compliance with current regulations on data protection. The access control will be

configured in such a way that there are two users with the project administrator role, who will be in charge of authorizing the access of the study personnel, as necessary, and with access levels according to the roles and responsibilities. The electronic forms that will be used for data upload will be specifically designed for this study. The data will be entered by the researcher at the recruitment center, via the web. The personnel in charge of entering the data will be trained in the use of RedCap for this purpose.

The study data corresponding to the Follow-up stage will be collected on paper-based forms. The forms will contain validated questions usually used in previous clinical studies.

At the sites, the anonymised paper-based forms will be scanned by trained personnel and stored in a secure location to protect sensitive information from unauthorized access. All anonymized digital forms, CCTA images, genetic data and laboratory reports will be encrypted and stored on a central outsourced AWS server. The access will be configured in such a way that there are two owners with the project administrator role, who will be in charge of authorizing the access of the study personnel, as necessary, and with access levels according to the roles and responsibilities.

A random quality check will be implemented on a sample of completed forms for accuracy and completeness to ensure that the data collected is reliable.

The study data will then be stored on a central outsourced server (AWS).

b. Data Entry

Trained and certified personnel will enter the digital data in an Excel format document located in the AWS server.

The following quality controls will be carried out:

- Validation rules generated according to the nature of the variables, programmed through the data validation modules available in Excel.
- Query generation according to pre-established validation rules, to be answered by researchers on the sites.

- Manual design of explanatory queries, to be answered by the researchers on the sites.
- Registration system, history and query control (queries).
- Periodic reports on the status of data entry, query generation and response, on a weekly basis.

Once data has been entered into a digital system, the physical forms will be properly filed to protect sensitive information.

c. Data security control: auditing and monitoring

Monitor and log activity within the AWS environment will be conducted regularly reviewing logs to detect unauthorized access or suspicious activity.

Regular data backup and disaster recovery will be automatically implemented using AWS Backup, in order to ensure the availability and integrity of study data. All the security processes will be performed by personnel certified in data security best practices, capable of handling sensitive information, how to identify phishing attacks, and how to report security incidents. Regular risk assessments and vulnerability scans will be conducted to identify potential threats and vulnerabilities in the AWS environment in order to implement the necessary controls to mitigate the risk.

d. Elaboration of the manual of procedures

A manual of procedures will be developed where the procedures for the implementation of the baseline data collection process, blood extraction, data management and storage and follow-up will be described.

e. Training and certification

In order to participate in the study, all staff must attend a training session prior to the start of fieldwork. Training sessions will include all aspects of the protocol and procedures manual regarding enrollment, blood samples management, data management, management of an adverse event, follow-up, and measurement procedures, data entry and data security. Those who have acquired the expected skills will be certified to carry out the study procedures. Staff will be retrained on a regular basis.

f. Site Monitoring Visits and Audits

Monitoring visits and audits will be conducted at the study sites in order to follow up on the progress of the fieldwork, identify problems and carry out retraining if necessary.

